### 2.3 Sample Size

Based on the results of the preceding DEPSCREEN-INFO trial (Löwe et al., 2016), the study is powered to detect a small mean difference (Cohen's  $f = 0.118$ ) in the primary outcome (depression severity) in any pairwise comparison between all three study arms. The calculation is based on a global one-way ANCOVA adjusted for baseline depression severity, with an alpha of 0.05 (two-sided) and a power of 80%. It results in a needed sample size of  $n = 233$  participants per group (PASS, 2008). To allow for an estimated drop out of 35% (c.f. Christensen et al., 2009), 358 participants per group are recruited (1074 in total).

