### 1.2 Study Objective

The study objective is to determine whether automated feedback after internet-based depression screening reduces depression severity as compared to no feedback.

**Primary Hypothesis:** The depression severity 6 months after screening is lower in at least one of the two feedback study arms (STANDARD FEEDBACK and/or TAILORED FEEDBACK) as compared to the NO FEEDBACK study arm.

**Secondary Hypothesis:** The depression severity 6 months after screening is lower in the TAILORED FEEDBACK arm as compared to the STANDARD FEEDBACK arm.

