### 2.4 Framework

The DISCOVER study is a superiority trial, testing pairwise comparisons between three study arms. All hypotheses are formulated two-sided and test for differences. To show superiority, we additionally look at the point estimate and the two-sided 95% confidence interval.

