### 5.3 Efficacy Evaluation

#### Analysis of Primary Endpoint

A multilevel model incorporating the participants as a random term is applied to the repeated measures in the same participant, including the factor group and the baseline value as a covariate. The primary analysis is performed within the framework of this model as an ANCOVA of the PHQ-9 change scores (T0 to T3-difference), with subsequent pairwise comparisons of interventions by test of the corresponding contrasts. The primary analysis is performed in the respective FAS population. The pairwise comparisons are done if the global test of group ( $H_0$ : all means are equal) could be rejected. Each test will be performed at a two-sided level of alpha = 0.05. This closed testing principle will ensure a family-wise error level of 5%.

Absolute, and relative frequencies of missing observations are presented both overall and separately for the randomized groups.

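### Section 2.3 claims power for any pairwise comparison, but 233 per group is the sample size for the global test, and at f = 0.118 single contrasts have less power, some far less

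*SAP*

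**What the plan says.** Section 2.3 of the SAP states that "the study is powered to detect a small mean difference", given as Cohen's f = 0.118, "in the primary outcome (depression severity) in any pairwise comparison between all three study arms". The next sentence names the basis: "The calculation is based on a global one-way ANCOVA adjusted for baseline depression severity", with two-sided alpha 0.05 and 80% power. The result is 233 participants per group, raised to 358 for 35% dropout. The section gives no pairwise difference, standard deviation or pattern of means.

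In section 5.3 (Analysis of Primary Endpoint) the contrasts sit behind a gate: "The pairwise comparisons are done if the global test of group" is rejected. On the level it adds: "Each test will be performed at a two-sided level of alpha = 0.05".

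Section 2.4 describes the trial as "testing pairwise comparisons between three study arms". In section 1.2 the primary hypothesis is that severity is "lower in at least one of the two feedback study arms" than without feedback. The secondary hypothesis is that it is lower with TAILORED than with STANDARD feedback.

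**The concern.** The two sentences in section 2.3 describe different properties. Power of the global test is the chance of rejecting equality of all three means. Power of a pairwise comparison is the chance of showing that two named arms differ, and here it also requires the global test to reject first. One does not follow from the other, because a single value of f is compatible with many sets of pairwise differences.

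The trial is framed around pairwise comparisons, and one of them, TAILORED versus STANDARD, is a hypothesis of its own. A reader of section 2.3 could credit that comparison with 80% power and take a non-significant result as good evidence of no difference.

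**Working it through.** **Inputs.** From section 2.3: f = 0.118, two-sided alpha 0.05, power 80%, n = 233 per group. From section 2.1: three arms, 1:1:1. From section 5.3: contrasts tested at 0.05 only after the global test rejects. Assumed, because the SAP does not give it: the pattern of the three means, so the whole range of patterns with f = 0.118 is covered. Differences are in units of the ANCOVA residual SD.

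**1. The plan's own figure.** Total N = 3 × 233 = 699. The noncentrality is λ = N × f² = 699 × 0.118² = 9.73. With three groups and one covariate the degrees of freedom are 2 and 699 − 4 = 695. The noncentral F distribution gives 80.2% power at 233 per group (80.1% at 232, 79.9% at 231). So 233 is a correct figure for the global test.

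**2. What f implies for pairs.** Let D be the distance between the outer means and let the middle mean lie at rD from the nearer end, with r from 0 to 0.5. Then f² = D²(2 − 2r + 2r²)/9.
- r = 0 (two equal arms, one apart): D = 3f/√2 = 0.250 SD. The other two arms do not differ.
- r = 0.5 (equal spacing): D = f√6 = 0.289 SD. Each adjacent pair differs by 0.1445 SD.

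The smallest gap, rD, rises with r, so at f = 0.118 it can never exceed 0.1445 SD.

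**3. Gated power of each contrast.** Simulation with 2,000,000 trials per pattern and 233 per arm: global F at 0.05, then t contrasts with pooled variance at two-sided 0.05. A contrast counts only if the global test also rejects.

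| r | Widest | Middle | Smallest |
|---|---|---|---|
| 0 | 72.1% | 72.1% | 4.9% (null pair) |
| 0.1 | 75.0% | 68.1% | 5.8% |
| 0.2 | 77.1% | 62.3% | 8.9% |
| 0.3 | 78.5% | 54.4% | 14.7% |
| 0.4 | 79.3% | 44.5% | 23.1% |
| 0.5 | 79.5% | 33.5% | 33.6% |

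At r = 0.5 the middle and smallest contrasts are the same size and differ only by simulation error. At least one contrast is significant in 80.3% of trials at every r. All three are significant in 1.6% (r = 0) to 5.3% (r = 0.5).

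**4. How much is due to the gate.** Without it the widest contrast has 77% (r = 0) to 88% (r = 0.5), so its shortfall at equal spacing comes from the gate. The smallest contrast has at most 34.4% even ungated. For 80% ungated power, 0.1445 SD would need 752 per group and 0.250 SD would need 251.

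**5. Other readings of the target difference.** If f is read as a two-group f, the difference is 2 × 0.118 = 0.236 SD, and gated power for that pair is 60% with the third mean midway and 66% with it at one end. If the target is a pair 0.250 SD apart, the corresponding figures are 66% and 72%.

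**The case against.** The strongest reply is that the sentence can be read in ways that are true or nearly so.

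- **A pair that differs by the target amount.** The least favourable position of the third mean is midway, where f = 0.118 corresponds to a difference of 0.289 SD. With that difference held fixed, gated power for the pair is 79.4% with the third mean midway and 84.9% with it at one end, and by symmetry this applies to any pair, TAILORED versus STANDARD included. This stands as arithmetic. But the SAP never states 0.289 SD, and f = 0.118 fits a 0.250 SD shift of one arm from two equal arms just as well (0.25 × √2/3 = 0.118).
- **At least one pair.** The 80% then holds, and this reading suits the primary hypothesis. It assures no particular contrast, and the text does not show that it is meant.

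It can also be said that the next sentence discloses the global basis, that 233 is correctly computed, that planning details may sit in the protocol, and that the sample size was long fixed when the SAP was finalised. All of this limits the consequences. Section 2.4 helps too: "we additionally look at the point estimate and the two-sided 95% confidence interval". An interval shows what the data exclude whatever the planned power was. None of this makes the pairwise claim follow from the calculation given for it.

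**Conclusion.** The concern holds. The 80% belongs to the global test. Taken as a statement about each comparison at f = 0.118, the sentence in section 2.3 cannot be true: the widest gated contrast has 72% to 79% power and the smallest at most 34%.

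The figures assume 233 analysed participants per arm, f on the ANCOVA residual scale (the scale on which 233 reproduces) and illustrative patterns of means. If all 358 per arm were analysed, the widest gated contrast would have 90% to 94% and the smallest still at most 49%.

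The defect lies in the stated property. The sample size, the tests and the error control are unaffected, and the practical risk is confined to how a non-significant contrast, above all TAILORED versus STANDARD, is interpreted. The statement should be corrected.

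**What to change.** Leave n and the analysis as they are and restate section 2.3, for example:

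> With 233 participants per group, the global ANCOVA test of group has 80% power at Cohen's f = 0.118 (alpha 0.05). Pairwise contrasts are tested only after the global test rejects. Their power depends on the pattern of means and is not 80% for every comparison, including TAILORED versus STANDARD.

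Then add the pairwise difference or pattern of means that was assumed, with the gated power of each contrast under it. If that assumption can no longer be recovered, give only the figures for f = 0.118 shown above, marked as illustrative. As the SAP is already final, the clarification can be recorded as an amendment or note and carried into the report.

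The cost is wording, plus a stated power property that is slightly less favourable.

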### 2.4 Framework

The DISCOVER study is a superiority trial, testing pairwise comparisons between three study arms. All hypotheses are formulated two-sided and test for differences. To show superiority, we additionally look at the point estimate and the two-sided 95% confidence interval.

### 2.5 Statistical Interim Analyses and Stopping Guidance

No interim analysis is conducted.

## 2.6 Timing of Outcome Assessments

**Table 1. Measures and assessment time points for endpoints**

Measures	T0	T1	T2	T3
Primary outcome				
Depression severity, PHQ-9	x		x	x a
Secondary outcomes / other outcomes				
Depression diagnosis by a health care professional				x
Guideline-based depression care (psychotherapy and/or medication)				x
Depression-related health behaviour (e.g. information-seeking)				x
Anxiety severity, GAD-7	x			x
Somatic symptom severity, SSS-8	x			x
Health-related quality of life, EQ-5D-5L	x			x
Illness beliefs, Brief IPQ	x		x	x
Intervention adherence	x			
Critical life events				x b
Depression diagnosis, SCID		x b		x b
Adverse events				x b
Characteristics				
Sociodemographic data	x			
Medical data	x			
Risk factors for depression onset	x			

*Note.* T0 = before randomisation (The randomization takes place immediately after the T0 assessments are performed); T1 = 2 days after randomisation; T2 = 1-month follow-up, T3 = 6-months follow-up; PHQ-9 = Patient Health Questionnaire-9; EQ-5D-5L = EuroQol-5D 5-L; GAD-7 = Generalized Anxiety Disorder-7; SSS-8 = Somatic Symptom Scale-8; SCID = Structured Clinical Interview for DSM-5 Disorders; Brief IPQ = Brief Illness Perception Questionnaire.

a Primary outcome; b Measures assessed via telephone interview.

## 2.7 Timing of Final Analysis

The final analysis of the DISCOVER trial takes place as soon as the final visit of the last participant is completed, the data are collected, the queries are processed, and the database is locked. According to our current milestone plan, the final data transfer will take place early October 2022. This is followed by the final analysis.

## 3 Statistical Principles

### 3.1 Confidence Intervals and *P* Values

All applicable statistical tests are two-sided and are performed using a 5% significance level. All confidence intervals presented are 95% and two-sided. Analyses of secondary, other and safety outcomes are performed exploratory without adjustment for multiple testing.

### 3.2 Intervention Adherence and Protocol Deviations

#### Intervention Adherence

Adherence will be defined using feedback reading time  $\geq 15$  sec (yes / no) and/or download of feedback form.

#### Protocol deviations

Major protocol deviations are defined as follows:

- Participants that did not adhere to or did not receive the intervention (feedback reading time  $< 15$  sec or no download of feedback form)
- Participants that have participated repeatedly for whatever reason
- Participants that report having participated in the study before
- Participants that report not having answered the survey seriously
- Participants with a baseline survey completion time  $< 2$  min
- Participants with an invalid email address

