## 2 Study Methods

### 2.1 Trial Design

The DISCOVER trial is designed as an internet-based, observer-blinded, stratified randomized controlled clinical trial with three parallel groups (1:1:1), which is conducted nationwide in Germany.

Study arms:

- No feedback: The participants do not get any feedback on their screening result.
- Standard feedback: Participants receive standardized feedback comprising the following four sections 1) the depression screening result, 2) a note to seek diagnostic consultation by a health professional, 3) brief general information on depression and 4) information on depression treatment.
- Tailored feedback: Participants receive standard feedback tailored to their individual symptom profile, illness perceptions and preferences. Details regarding the tailored feedback arm are described in the published study protocol.

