#### Per Protocol Population (PP)

The Per Protocol population is a subset of the FAS and includes only participants who have no major protocol violation (see chapter 3.2).

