#### Evaluated for Safety Set (EFS)

All randomized participants who were provided directly after the randomization with feedback or a 'thank you' note (no feedback) will be included into the Evaluated for Safety (EFS) set. Only participants who were reached by phone 6 months after randomization could be asked regarding possible adverse events.

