## 5.7 Differences to Trial Protocol

In contrast to originally stated in the study protocol, the USE will not be analysed. A change of the USE questionnaires occurred during the study.

Furthermore, website use will not be analyzed as a variable on its own, but will be used for the evaluation of major protocol deviations and intervention adherence (see 3.2).

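### SAP 3.2 counts reading or downloading the feedback as adherence, yet makes doing only one of the two a major deviation; the rule also names no arm

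*SAP*

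**What the plan says.** SAP 3.2, under Intervention Adherence, defines adherence by a feedback reading time of at least 15 "sec (yes / no) and/or download of feedback form".

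The next subsection, Protocol deviations, lists six major deviations. The first is "Participants that did not adhere to or did not receive the intervention", spelled out in brackets as a reading time under 15 "sec or no download of feedback form". No arm is named.

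The PP population in SAP 3.3 "includes only participants who have no major protocol violation" and takes the list from 3.2. SAP 5.3 (Sensitivity Analyses) repeats the primary endpoint analysis in that population. SAP 5.7 adds that website use "will be used for the evaluation of major protocol deviations and intervention adherence (see 3.2", so the same log data feed both rules. Table 1 in SAP 2.6 lists intervention adherence as an assessed measure.

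On the control arm, SAP 2.1 states: "The participants do not get any feedback on their screening result". The safety set in SAP 3.3 describes participants as "provided directly after the randomization with feedback or a 'thank you' note (no feedback", so controls receive a note rather than feedback.

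**The concern.** The two subsections describe one concept, since the deviation criterion itself speaks of not adhering. One should therefore be the logical complement of the other. If either behaviour is enough to adhere, a participant fails to adhere only when both are absent. The deviation criterion instead fails a participant when either is absent.

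The same person could then be reported as adherent and be removed from PP for not adhering. The PP repeat of the primary analysis would not describe the population that the adherence figures describe. If the choice of rule is left to the analysis stage, it could also be made with results in view.

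Separately, because no arm is named, a literal reading makes every NO FEEDBACK participant a deviator: none of them has a feedback form to download. PP would then hold no controls, and the feedback versus no-feedback contrasts could not be estimated in it.

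**Working it through.** The SAP gives no figure on this point to reproduce. The check is a truth table built from the two subsections of 3.2.

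**Notation.** R = reading time of at least 15 seconds; D = feedback form downloaded.

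- Adherence (Intervention Adherence, inclusive reading): R or D. Its negation is (not R) and (not D).
- Major deviation (Protocol deviations): (not R) or (not D).

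| R | D | Adherent, *and/or* inclusive | Adherent, *and/or* read as *and* | Major deviation |
|---|---|---|---|---|
| yes | yes | yes | yes | no |
| yes | no | yes | no | yes |
| no | yes | yes | no | yes |
| no | no | no | no | yes |

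**Inclusive reading.** One of four combinations is non-adherent and three of four are major deviations, so 3 − 1 = 2 of 4 are adherent yet excluded from PP.

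**Strict *and*.** Three of four are non-adherent and the same three are deviations, so 3 − 3 = 0 of 4 conflict.

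**Which reading the SAP supports.** SAP 1.2 uses the same connective to spell out "at least one of the two feedback study arms (STANDARD FEEDBACK and/or TAILORED FEEDBACK", which is the inclusive sense. Nothing in 3.2 or 5.7 says otherwise.

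**Share of participants.** With r = P(R) and d = P(D), the affected share of a feedback arm is P(exactly one) = r + d − 2·P(R and D). The SAP gives neither r, d nor their joint probability. As an assumption only, take r from 50% to 90%, d from 10% to 50%, and independence, so that P(R and D) = r·d:

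- Affected share: from 0.5 + 0.1 − 2(0.05) = 0.50 to 0.9 + 0.1 − 2(0.09) = 0.82.
- Passing this criterion as written, r·d: from 0.5 × 0.1 = 0.05 to 0.9 × 0.5 = 0.45.
- Passing it if the rule were the complement of the inclusive definition, 1 − (1 − r)(1 − d): from 1 − 0.5 × 0.9 = 0.55 to 1 − 0.1 × 0.5 = 0.95.

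Independence matters. If exactly the same people read and download (r = d = P(R and D) = 0.5), the affected share is 0.5 + 0.5 − 2(0.5) = 0. These figures show that the operator can decide who is in PP; they do not estimate how many are affected.

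**Arms.** The criterion can apply sensibly only to 2 of the 3 arms. Of the six listed deviations, 6 − 1 = 5 remain for NO FEEDBACK participants.

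**The case against.** The strongest reply is that the adherence sentence only names the variables to be used, and that the deviation list then sets the cut. On that view the first text is loose rather than contradicted, and since SAP 3.3 takes PP from the deviation list, membership in the feedback arms is already determined. The second half of this stands: the deviation list does give one literal PP rule for those arms. The first half does not remove the problem. If the adherence sentence is not a rule, the SAP has no adherence rule of its own, and *and/or* still needs the same correction.

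A second reply is that nobody would apply a feedback-reading criterion to people who received no feedback. That is right. The flow diagram in SAP 4.3 counts no feedback as a received allocation, the safety set recognises the note, and the PP repeat in 5.3 needs all three arms. This part is a clarification only.

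A third reply is that little depends on PP in a superiority trial whose primary set is the FAS, that adherence has no analysis of its own in 5.3, and that two of four cells is not a count of people. The limited reach and the unknown size are conceded. But adherence is listed as a measure in Table 1 and 5.7 plans its evaluation, so two conflicting classifications would be produced from the same data.

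**Conclusion.** The concern holds. On the ordinary inclusive reading of *and/or*, the adherence definition and the major-deviation criterion disagree for participants who show exactly one of the two behaviours: 2 of 4 combinations, in 2 of 3 arms. The conclusion depends on that reading; under a strict *and* there is no conflict, but the SAP does not state one. The share of participants affected cannot be derived from the SAP.

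The missing arm restriction is a lesser point of wording, because the intention is evident from other sections.

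The consequence is limited to the PP sensitivity analysis of the primary endpoint and to the adherence and deviation counts. The FAS primary analysis, the closed testing procedure and the sample size do not change. This should be corrected, but it does not threaten the trial's main conclusion.

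**What to change.** Issue a dated SAP amendment, before group-level outcomes are analysed, that replaces the two texts in 3.2 by one Boolean rule and its exact negation. The sponsor chooses which:

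- **Either behaviour suffices:** keep the adherence definition and change the deviation criterion to a reading time under 15 seconds *and* no download.
- **Both are required:** change *and/or* to *and* in the adherence definition and leave the deviation criterion as it is.

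In either case, limit this criterion to the STANDARD FEEDBACK and TAILORED FEEDBACK arms, and state that NO FEEDBACK participants are assessed for PP on the other five criteria.

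The cost is one operator and one phrase. Website-use data are already assigned to both evaluations in 5.7, so no new data are needed. Timing is the only constraint: version 1.0 is final as of 30.09.2022 and SAP 2.7 plans the final data transfer for early October 2022.

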### 3.3 Analysis Populations

#### Full Analysis Set (FAS)

The primary analysis is based on the full analysis set (FAS). It is as complete as possible and as close as possible to the Intention-To-Treat (ITT) principle which includes all randomized participants, as belonging to their randomization arm, regardless of whether they received the feedback or not, or whether other protocol violations are known. For the FAS at least a valid baseline and one valid post-baseline value of the primary outcome needs to be available.

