### Other Outcomes

The following other endpoints are continuous outcomes:

- Brief IPQ single items (difference from baseline (T0) is calculated for 1 month (T2) and 6 months after randomization (T3))
- Critical life events at T3 (sum score for positive and negative life events, respectively)

The following other endpoints are binary outcomes. For these, no difference to baseline (T0) is calculated:

- SCID at T1 and T3

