#### Analysis of Secondary Endpoints

The secondary endpoint analyses are performed in the respective FAS population. All secondary endpoints are compared and statistically assessed for descriptive purposes and not in a confirmatory sense. The aim of the analysis is an exploratory data analysis, not hypothesis testing or generation of evidence for the efficacy. No attempt is made to adjust for the p-values for multiple testing.

Mean, standard deviation, first and third quartile, minimum and maximum for the continuous variables and absolute and relative frequencies for the categorical and binary variables are presented both overall and separately for the randomized groups for each time point. Number of missing observations are presented for the randomized groups separately for each time point. All summary tables are structured with a column for each group (tailored feedback, standard feedback, no feedback) and a total column.

Multilevel linear models with differences from baseline as outcome, incorporating the participants as a random term, are applied to the repeated measures in the same participant, including the factor group, time point, and the baseline value as a covariate. The interaction between time and the group is determined. If it is not significant, it is eliminated from the model. Adjusted means with 95% confidence intervals (CI) and p-values are reported.

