#### Analysis of other Endpoints

Other endpoints will be analysed, depending on the level of scale, as defined for the secondary endpoints. See chapter 5.3. The SCID will be analysed descriptively using summary statistics.

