## 5.4 Safety Evaluation

All adverse events will be analysed in the EFS using summary statistics and, if applicable, analysed using logistic regression.

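### By cross-reference the SCID at T1 and T3 and critical life events default to the FAS, so completed telephone interviews are dropped when no follow-up PHQ-9 was given

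*SAP*

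**What the plan says.** Five places in the SAP bear on this.

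- **Section 3.3, FAS:** "For the FAS at least a valid baseline and one valid post-baseline value of the primary outcome needs to be available". The primary outcome is the PHQ-9.
- **Section 2.6, Table 1:** the note gives the timing, "T1 = 2 days after randomisation; T2 = 1-month follow-up, T3 = 6-months follow-up". The PHQ-9 is marked at T0, T2 and T3 only. The SCID is marked at T1 and T3, and critical life events and adverse events at T3. These three carry the footnote "Measures assessed via telephone interview"; the PHQ-9 does not.
- **Section 5.1, Other Outcomes:** "SCID at T1 and T3" is listed as a binary outcome for which no difference from baseline is formed. Critical life events are a T3 sum score.
- **Section 5.3:** for secondary endpoints, "The secondary endpoint analyses are performed in the respective FAS population". For the rest, "Other endpoints will be analysed, depending on the level of scale, as defined for the secondary endpoints", followed by "The SCID will be analysed descriptively using summary statistics". Neither of these last two sentences names an analysis set.
- **Section 5.4:** "All adverse events will be analysed in the EFS using summary statistics". The EFS, defined in 3.3, has no PHQ-9 follow-up condition, and its definition notes that only participants reached by telephone at 6 months could be asked.

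**The concern.** Membership of the FAS is decided at 1 month at the earliest. If the FAS is the set for the T1 SCID, an interview done on day 2 is kept or removed according to whether the participant answers a questionnaire weeks or months later. The T1 summary then describes later responders rather than the participants randomised and interviewed. Participants know their allocation (section 2.2), so response may differ by arm, and the arms could then be selected differently.

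The same condition reaches T3. Someone interviewed by telephone at 6 months who gave no PHQ-9 at T2 or T3 is left out of the SCID and life-events summaries although the data exist.

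A requirement for a post-baseline PHQ-9 makes sense for a PHQ-9 change score. It serves no evident purpose for a diagnosis taken by another mode, at another time, with no change from baseline calculated.

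**Working it through.** **Which set applies**

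1. Section 5.3 sends the other endpoints to the rules for secondary endpoints.
2. Those rules place the analysis in the FAS.
3. The FAS requires a PHQ-9 after baseline.
4. Table 1 offers that PHQ-9 only at T2 (1 month) or T3 (6 months).
5. No other defined set takes over. The per-protocol population is a subset of the FAS, and the EFS is assigned to adverse events.

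The FAS is therefore the only default the text provides for the SCID and critical life events.

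**The plan's own figures (section 2.3)**

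The plan needs 233 evaluable participants per group and allows for 35% dropout. 233 / (1 - 0.35) = 358.5, against 358 stated; 3 x 358 = 1074. The figures used below are 1074 randomised and 35% dropout.

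**Completed T1 interviews that the FAS condition would remove**

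Lost = 1074 x (share with no PHQ-9 at T2 or T3) x (T1 reach in that group).

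Kept = 1074 x (1 - that share) x (T1 reach in later responders).

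The SAP gives neither T1 reach nor T2 missingness. Assumptions: T1 reach of 40-60% in later non-responders and 70-80% in later responders, and 15-35% missing at T2. The 35% dropout is read as missing at T3.

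| Scenario | No follow-up PHQ-9 | Lost | Kept | Lost as share of T1 interviews |
|---|---|---|---|---|
| T2 and T3 missingness independent, 15% missing at T2, reach 40% / 70% | 1074 x 0.35 x 0.15 = 56 | 56 x 0.40 = 22 | 1018 x 0.70 = 713 | 22/735 = 3.0% |
| Independent, 35% missing at T2, reach 60% / 80% | 1074 x 0.35 x 0.35 = 132 | 132 x 0.60 = 79 | 942 x 0.80 = 754 | 79/833 = 9.5% |
| All dropouts also miss T2, reach 60% / 80% | 1074 x 0.35 = 376 | 376 x 0.60 = 226 | 698 x 0.80 = 558 | 226/784 = 28.8% |

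**Effect on the T1 summary**

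Shift in the reported SCID proportion = share lost x difference in proportion between later non-responders and later responders. With an assumed difference of 10 percentage points:

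- first row: 0.030 x 10 = 0.3 points;
- second row: 0.095 x 10 = 0.9 points;
- third row: 0.288 x 10 = 2.9 points.

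The shift is zero if the two groups have the same proportion.

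**T3 interviews**

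No figure can be given. The loss depends on how many participants are reached by telephone at 6 months with no PHQ-9 at T2 or T3, and the SAP contains nothing from which to estimate that.

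**The case against.** The strongest reply is that the SAP never expressly puts the SCID in the FAS. The cross-reference in 5.3 is worded around the level of scale, which points first to the statistical method. It cannot carry the secondary-endpoint model over whole, because critical life events have no baseline value. The SCID then has its own sentence, with no set. The word *respective* before FAS might suggest a set specific to each endpoint. All of this is fair as far as it goes: the assignment is by default, not by statement. But section 3.3 defines one FAS, tied to the primary outcome, and 5.3 uses the same word for the primary analysis. If another set was meant, the SAP does not say so, and the same sentence is needed.

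A second reply is that a common set keeps denominators consistent across tables, and that the selection would be partly visible: section 4.3 reports exclusions from the primary analysis with reasons, and 5.5 plans a drop-out analysis if applicable. That also stands, but neither restores the interviews that were removed.

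Three stronger readings are tempting and are not supported.

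- A reader might infer that all T3 telephone outcomes are subject to the FAS condition. Adverse events are not: 5.4 assigns them to the EFS.
- A reader might take 35% as the share without any follow-up PHQ-9. It is a planning allowance for dropout, and a T2 value alone is enough to enter the FAS.
- A reader might treat the T1 SCID as the trial's estimate of how many screen-positive participants have major depression. Section 1.2 states no such objective, and 1.3.3 lists the SCID only among other endpoints.

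**Conclusion.** The point holds as a low-severity defect. Read through its own cross-references, the SAP conditions the T1 SCID on a PHQ-9 given at least 1 month later, and conditions the T3 SCID and critical life events on a PHQ-9 they do not need. Adverse events show that the SAP can handle a telephone outcome without this condition; no reason is given for the different treatment.

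The size is not determinable from the SAP. The range of about 22 to 226 lost T1 interviews rests on assumed reach and assumed T2 missingness. Its top requires every dropout to have missed T2 as well. Its bottom assumes independence, which favours the plan because people who miss one follow-up tend to miss the next. The 0.3 to 2.9 point shift also needs the assumed 10-point difference. That T3 interviews can exist without a PHQ-9 rests on Table 1, which does not mark the PHQ-9 as a telephone measure.

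The SCID is only described, not tested, and the other outcomes are exploratory (section 3.1). The primary and secondary endpoints do not change.

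**What to change.** In section 5.3, under the other endpoints, state that the SCID at T1, the SCID at T3 and critical life events at T3 are summarised as randomised in all randomised participants with that interview completed, without requiring a post-baseline PHQ-9. Report the number interviewed per arm and time point as the denominator.

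The cost is one sentence in the SAP and a different filter for these tables. The downside is that their denominators will differ from those of the FAS tables, so each table should state its own.
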